There is increasing evidence for the importance of gut microbiota in risk of type 2 diabetes and other cardiometabolic diseases.⁶⁹ Additionally, dietary modifications, including changes in carbohydrate consumption, can lead to substantial changes in gut microbiome over short periods of time.^{70,71} Less is known about longer-term changes to the gut microbiota during the adoption of a low-carbohydrate diet and how these changes may influence cardiometabolic risk. We plan to collect stool specimens at baseline, 3 months, and at 6 months, for potential future studies on how this intervention affects the gut microbiome.

2.I. Continuous Glucose Monitoring

As HbA1c is a marker of weighted average glucose over the past 8 to 12 weeks, it does not explicitly capture short-term glycemic excursions or variability. It has been theorized that such fluctuations may have an independent role in the development of diabetes complications.⁷² Though more evidence is needed, research has found relationships of higher glycemic variability with coronary artery disease (CAD) and microvascular outcomes in type 2 diabetes (T2D).^{73,74} This suggests that improved control of extreme glucose excursions, particularly postprandially, may help to reduce risks of such complications.⁷⁴

In one study of a low-calorie, low-carbohydrate diet compared with a low-calorie, low-fat behavioral dietary intervention among individuals with T2D, there was evidence that some markers of glycemic variability were further reduced in the low-carbohydrate arm compared with the low-fat arm (assessed by 48-hour continuous glucose monitoring) at 6 months, 1 year, and 2 years.^{35,38,75} However, there is not prior work assessing how a behavioral intervention aimed at reducing carbohydrate consumption affects mean glucose, glucose exposure above the set-point of 100 mg/dL, glucose excursions, or glycemic variability as measured by continuous glucose monitoring among individuals with untreated T2D or at high risk of T2D.

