Given this background, we will use continuous glucose monitors (CGM) to collect data for up to 14 days on glucose levels at the end of the 6-months study and will compare mean 24-h glucose among those in the intervention group compared with mean 24-h glucose among those in the control group. We will also measure other markers of glycemic exposure, such as glycemic variability (mean amplitude of glycemic excursions (MAGE), standard deviation of glucose, coefficient of variation) and mean 24-hour glucose during wake-time (6:00 AM to 12:00 AM), and during sleep-time (12:00 AM to 6:00 AM).

2.I. Clinical and public health significance of the proposed study

Prediabetes, or intermediate hyperglycemia, is a marker of high risk of developing T2D and other complications. Due to increasing prevalence of T2D and associated morbidity and mortality globally, a better understanding of dietary approaches to delay progression to T2D or to promote reversion to normoglycemia is a high public health priority. This study proposes to assess the effect of a behavioral intervention promoting a low-carbohydrate/high-unsaturated fat dietary pattern (initial target <40 g digestible carbohydrates, final target <60 g digestible carbohydrates) on HbA1c, a marker of glycemic control, and other metabolic risk factors. Building from prior findings from clinical and observational studies, we will develop a dietary intervention that promotes the consumption of non-starchy vegetables, plant-based oils, fish, poultry, and mixed nuts, that are thought to reduced risk of T2D or CVD. Participants assigned

to the intervention will be trained in behavioral techniques that will provide capacity to maintain dietary changes long after study completion. Our outcome measures will assess the effect of this dietary intervention in a “real-life” setting as opposed to dietary modifications achieved in metabolic ward studies or through food prepared in research kitchens. Findings from this study may provide evidence in support of promoting alternative dietary styles among individuals with high T2D and CVD risk and could potentially be used to inform dietary interventions used in programs like DPP.

2.J. Innovation

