- Self-report of liver disease due to hepatitis or alcohol; osteoporosis; untreated thyroid disease; gout; or cancer (other than non-melanoma skin cancer) requiring treatment in the past year, unless prognosis is excellent
- Factors that may affect HbA1c:
 - Hemoglobin <11 mg/dL (cutpoint for moderate-to-severe anemia, which could lead to falsely elevated or lowered HbA1c)¹⁰⁰
 - Recent blood donation or blood transfusion (self-report, past 4 months)
 - Human Immunodeficiency Virus (self-report)¹⁰¹
- Self-reported history of intensive care unit stay due to Coronavirus Disease 2019 (COVID-19) in the past three months, as severe COVID-19 may affect blood glucose levels
- Allergies to nuts
- For women, current pregnancy, breastfeeding, or plans to become pregnant during the study
- Consumption of ≥21 alcoholic drinks per week or consumption of ≥6 drinks per occasion
- For the CGM collection at the end of the study period only: known allergy to adhesives or other products involved with CGM use (e.g., skin disinfectants), current pregnancy, currently on hemodialysis or peritoneal dialysis, or people with other implanted medical devices (e.g., a pacemaker)
- Current or planned residence making it difficult to meet trial requirements (due to distance from study site and/or challenges regularly traveling to site)
- Current participation in another lifestyle intervention trial or a pharmaceutical trial
- Participation of another household member in the study; employees or persons living with employees of the study
- Other concerns regarding ability to meet trial requirements, at the discretion of the principal investigator or study coordinator

7. Recruitment and Randomization

7.A. Recruitment

We will recruit study participants from the greater New Orleans area. The initial focus of our recruitment will be mass mailing of individuals in the greater New Orleans area and recruitment through placing flyers and brochures in the community. If community-based recruitment is not successful or cost-effective, we will recruit out-patients from the Ochsner Health System and Tulane Medical Center (TMC), from which our group has prior experience recruiting patients. For this recruitment, we will focus on electronic searches of medical records and laboratory databases. We will also carry out targeted solicitation of referrals from physicians who care for patients likely to meet our inclusion and exclusion criteria.

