Clinical and laboratory staff members who assess outcomes will be blinded to the intervention assignment of participants. As this is a dietary intervention trial, study participants, and study staff members who conduct the intervention cannot be blinded to the intervention assignment. Participants will be instructed to avoid sharing knowledge of their treatment assignment with data collection staff members. We will have intervention visits and data collection study visits on different days and in separate locations. Data collectors will also use verbal cues and visual props to remind participants not to disclose treatment assignment. Investigators will be blinded to intervention assignment.

7.D. Safety Considerations

Participants with HbA1c >7.9% will be referred to a clinician for follow-up¹⁰², though we will continue to collect data on these participants.

8. Dietary Intervention Program

8.A. Low-carbohydrate dietary intervention group

Participants randomized to the low-carbohydrate intervention group will receive counseling aimed at reducing carbohydrate consumption. Phase I (*Go Low*) will occur for the first 3 months, with a goal of <40 g digestible carbohydrates per day. Key recommended foods will include: non-starchy vegetables, fish, poultry, lean meat, eggs, olive oil and other plant-based unsaturated oils, unsweetened/unsalted nuts and seeds, nut butters, and avocados. We will recommend moderate consumption of cheese and unsweetened Greek yogurt and low-carbohydrate milk. During Phase I, we will recommend limiting or avoiding other dairy, fruits, legumes, beans, and grains. Phase II (*Keep it Low*) will run from months 4 through 6. The net carbohydrate goal for this phase will be <40 g to <60 g, with the objective to choose a target that is as low as possible (e.g., as close to <40 g as possible). At 3 months, we expect different participants will have different levels of intake, with some consuming <40 g of net carbohydrates and others consuming levels higher than 60 g net carbohydrates per day. We have designed the intervention to accommodate various scenarios, with the goal of achieving as low of an intake as possible. For participants who consume >60 g per day, we will recommend they aim to either reduce or maintain carbohydrate intake.

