Strategies for measuring compliance: For the low-carbohydrate diet, adherence will be assessed through measurement of urinary ketones at 3-month visit and 6-month TV. Study staff will make all reasonable effort to maintain adherence of participants to the visit schedule and diet intervention.

Strategies for improving compliance:

- At the screening visit, we will ask participants who does most of the cooking in their households and how often they eat outside of the home. Results from the screening visit will help to select a group of cooperative study participants.
- Visits will be scheduled at the participants' convenience and to minimize waiting time and trips to the clinic; reminder calls, texts or emails (chosen based on participant preference) will also be made prior to clinic visits.
- We will hire enthusiastic staff who have good interpersonal skills.
- Participants will receive \$40 gift cards for use at food stores or retailers when they complete each study visit, for a maximum of \$120 over the study period.
- Participants will receive \$25 gift cards when they return the stool specimens, for a maximum of \$75 over the study period.

- Participants will receive a \$25 gift card when they return the continuous glucose monitor, for a maximum of \$25 over the study period.
- Participants will be offered small gifts (such as pens or magnets with study logo) to encourage compliance and adherence to the study protocol.
- Participants will be provided with recipes, shopping lists, and food samples for the intervention diet.

9. Safety of Dietary Intervention

On the low-carbohydrate diet, participants will be encouraged to primarily focus on replacing carbohydrates (particularly highly refined carbohydrates) with foods such as non-starchy vegetables, olive oil and other plant-based unsaturated oils, nuts and seeds, avocados, eggs, seafood, tofu, poultry, and lean meat. Consumption of more unsaturated fats, protein, and fiber will be recommended. Participants will not be encouraged to increase consumption of saturated fats and will be advised to avoid consumption of trans fats.

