**The CGM will be worn for up to 14 days prior to the 6-month TV and returned at the TV or by mail. Participants will come in for a 6-month CGM visit (prior to the 6-month TV) to have the CGM inserted.

10.A.1. Screening/baseline visits:

Participants will be pre-screened by phone or in-person by study staff to confirm eligibility for the Screening Visit. An approved questionnaire will be used to ensure the patient is eligible to attend the in-clinic screening visit, and the patient will be scheduled thereafter.

At the screening visit (SV), participants will provide informed consent for the screening and main study. Study staff will schedule the SV and randomization (RZ) visit at least 2 days apart. If a participant is eligible based on the screening visit, he or she should be scheduled for the RZ once a sufficient group of eligible individuals has been recruited. Participants should be scheduled for the RZ at least 2 days and no more than two weeks after the screening visit.

At the screening visit, we will collect information on inclusion/exclusion criteria, medication use, and demographics. At this visit, we will also have participants complete a compliance form,

to assess their ability to complete the study and attend all intervention and study visits. We will also measure blood pressure, and take blood samples. Women will be asked if they are postmenopausal or if they had surgical sterilization (such as a tubal ligation). If not, they will be tested for pregnancy through a spot urine test; pregnant women will be excluded from the study. Blood samples will be collected for measurement of HbA1c, and, if not available from medical records in the past 3 months, serum creatinine and hemoglobin. These blood samples will be used for excluding individuals with HbA1c <6.0 or >6.9, eGFR ≤45 mL/min/1.73 m², or hemoglobin <11 mg/dL.

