10.A.2. Follow-up visits and final visit: A follow-up visit will occur at 3 months after randomization. A final visit will occur at 6-months post-randomization. These visits should be scheduled as close as possible to the 3-, or 6-months after randomization. At each visit, study staff will conduct dietary recalls and anthropometric measures, take 3 BP measurements, collect a fasting blood sample to measure HbA1c. At least one (and potentially both) 24-h recalls will be collected by phone. We will also collect samples for later measurement of glucose, insulin, lipid profile, and other potential future measurements. A spot urine sample will be collected to measure ketones and other markers. Participants will be asked to collect a stool specimen for potential use in future microbiome studies. Information about participants' nut consumption over the past 6 months will be collected at the 6-month TV. At study termination, we will mail participants and/or their physicians a summary of trial results and a record of participant BP, anthropometric measures, and laboratory data from the trial period. Throughout the study period, we will provide participants with their blood pressure and weight. We will request that, if possible, a participant who is prescribed a diabetes medication during the course of the study comes into the clinic for an additional separate supplemental visit for a fasting blood sample collection prior to starting the medication. Maintaining follow-up of all randomized participants is of utmost importance to ensure data integrity. In the event that a participant moves during the study we may request that the participant provides a fasting blood sample at a local LabCorp facility (this will be described on the informed consent form).

10.A.3. CGM 6-month visit: Individuals who are willing to wear the CGM prior to their 6-month termination visit will come to the research clinic approximately 2 weeks before their 6-month termination visit for their CGM visit. At this time, they will have a factory-calibrated CGM inserted just under the skin of the upper arm and activated.¹¹² If the CGM falls off of a participant prior to 14 days of wear, we may request that the participant (if willing) returns to the clinic for the CGM to be re-inserted. The CGM will be returned at the 6-month TV, or by mail.

10.B Study measurements

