10.B.8. CGM at 6 months: Approximately two weeks before their 6-month termination visit, participants willing to wear the CGM will come to the clinic to have their CGM inserted. This CGM has been found to be accurate compared with capillary blood glucose reference values over 14 days of wear.¹¹² This CGM records interstitial glucose every 15 minutes throughout the day for a period of up to 14 days. The sensor uses a thin, flexible filament inserted just under the skin to measure glucose and is read through near-field communication by touching the reader to the sensor. For quality control of the CGM data, a subset of participants who wear the CGM will be asked to wear two CGMs at the same time, one on each arm. Prior to insertion, one arm will be designated as the arm used for data collection and the other arm as a duplicate.

11. Quality Assurance and Quality Control

Throughout the study, we will implement rigorous quality assurance (QA) and quality control (QC) measures. We describe some of these approaches here.

11.A. Manual of procedures

We will develop a manual of procedures (MOP) based on the MOP successfully used in the MACRO behavior change clinical trial. The MOP will provide instructions and describe procedures for staff training and certification, participant recruitment, intervention counseling, study form completion and procedures, data entry, safety measures (e.g., methods for emergency participant/primary care physician contact).

11.B. Training and certification

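### CGM is a single, opt-in, month-6 measure with no baseline: analyse it by baseline-adjusted regression, label it exploratory, and report wear by arm

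*Combined protocol and SAP*

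**What the plan says.** Section 2.I (Continuous Glucose Monitoring) justifies CGM by a lack of prior work on "how a behavioral intervention aimed at reducing carbohydrate consumption affects mean glucose, glucose exposure above the set-point of 100 mg/dL", so the question is about the effect of the intervention. It then says that the investigators "will compare mean 24-h glucose among those in the intervention group compared with mean 24-h glucose among those in the control group", and lists further measures: MAGE, SD, coefficient of variation, and wake-time and sleep-time means.

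- **Timing.** The note to Table 3 says: "The CGM will be worn for up to 14 days prior to the 6-month TV and returned at the TV or by mail". Tables 3 and 4 show no baseline or 3-month CGM.
- **Who wears it.** Section 10.A.3: "Individuals who are willing to wear the CGM prior to their 6-month termination visit will come to the research clinic". Section 10.B.8 also restricts it to the willing. Section 6.A adds exclusions specific to CGM, beginning "For the CGM collection at the end of the study period only: known allergy to adhesives or other products involved with CGM use".
- **Blinding.** Section 7.C: "study participants, and study staff members who conduct the intervention cannot be blinded to the intervention assignment". Staff who assess outcomes are blinded.
- **Incentive.** Section 8.D offers a "gift card when they return the continuous glucose monitor", not limited to one arm.
- **Analysis plan.** CGM is absent from the outcome lists (sections 1, 4.A and 4.B), from Table 5 and from section 13.B. Section 13.B words intention to treat for primary and secondary outcomes. Section 13.B.2 models change from baseline, and plans imputation of missing outcomes as a sensitivity analysis without naming CGM.

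**The concern.** Two separate issues arise, and they differ in kind.

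**Precision.** With no CGM baseline, differences between people that existed before randomisation remain in the error term of a plain comparison of means. The change-score method used for the other outcomes is not available, and nothing is put in its place.

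**Selection.** Attending the CGM visit happens after randomisation, among people who know their arm. By then the diet arm has been scheduled for 11 in-person sessions and 7 calls (section 8.A), while controls have had written advice and optional sessions on unrelated topics (section 8.B). Wearing could therefore depend on arm, engagement or success with the diet. The plan defines no CGM analysis set, no reporting of uptake by arm and no handling of non-wearers.

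What is at stake is the reading of the CGM result. A wearers-only contrast set beside an intention-to-treat HbA1c result could be taken for a glycaemic benefit beyond HbA1c when part of it reflects who wore the sensor. The primary outcome and the sample size are not affected.

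**Working it through.** **1. The plan's own figure.** Table 5 gives a detectable HbA1c difference of 0.17% (SD 0.35, 142 analysed, 80% power, two-sided 0.05, unpaired t-test). With 71 per arm the t-test calculation gives 0.166%, which rounds to 0.17%. The normal approximation gives (1.960 + 0.842) × 0.35 × √(2/71) = 0.165%. The figure is reproduced. None is given for CGM, so the rest is in SD units and rests on assumptions.

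**2. Precision of the CGM comparison.** Detectable difference = 2.802 × √(2/m), for m wearers per arm out of 75:

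- 100% uptake, m = 75: 0.46 SD
- 80% uptake, m = 60: 0.51 SD
- 60% uptake, m = 45: 0.59 SD

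**3. Gain from baseline covariates.** The standard error is multiplied by √(1 − r²), where r is the joint correlation of the covariates with the CGM measure (assumed 0.3 to 0.6):

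- r = 0.3: √0.91 = 0.954, a reduction of about 5%
- r = 0.6: √0.64 = 0.80, a reduction of 20%

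At m = 60 the detectable difference falls from 0.51 SD to 0.51 × 0.954 = 0.49 SD, or to 0.51 × 0.80 = 0.41 SD.

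**4. Selection.** Let p be uptake in an arm and D the wearer-minus-non-wearer mean in that arm. Wearers differ from the whole arm by (1 − p)D. The wearers-only contrast (diet minus control) therefore differs from the all-randomised contrast by

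(1 − p_diet) × D_diet − (1 − p_control) × D_control.

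Negative values favour the diet. The last column is the chance of a significant result when the true effect in all randomised participants is zero. All values of p and D are assumed.

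| Uptake diet / control | D diet | D control | Bias (SD) | Type I error |
|---|---|---|---|---|
| 95% / 95% | −0.5 | −0.5 | 0 | 5.0% |
| 95% / 95% | −0.5 | +0.5 | −0.05 | 6.0% |
| 80% / 80% | −0.5 | −0.5 | 0 | 5.0% |
| 80% / 80% | −0.5 | 0 | −0.10 | 8.5% |
| 80% / 80% | −0.5 | +0.5 | −0.20 | 19.5% |
| 80% / 60% | −0.5 | −0.5 | +0.10 | 8.0% |
| 80% / 60% | −0.5 | +0.5 | −0.30 | 33.1% |

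In mg/dL: if 30% of the diet arm decline, decliners run 2 to 10 mg/dL higher than wearers, and controls show no selection, the bias is 0.30 × 2 = 0.6 to 0.30 × 10 = 3 mg/dL in favour of diet. With the same decline rate and the same gap in controls it is zero.

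**5. Can non-wearers be modelled?** At 30% declining there are 0.30 × 75 = 22.5 decliners per arm. A within-arm model for wearing that used baseline and 3-month HbA1c, fasting glucose and weight (six predictors) would have 22.5 / 6 = 3.75 decliners per predictor. Such weights would be unstable.

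**The case against.** A reader might infer that the CGM component cannot show how the intervention affects glucose, because there is no baseline and the wearers chose themselves. The documents do not support that. Allocation is 1:1 and random, so a post-treatment comparison without a baseline is valid in expectation. Only the decision to wear is self-selected, and its effect depends on an uptake that the plan does not state and that could be high and balanced.

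Other points against the concern:

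- Section 2.I is background text. It names no estimator and does not rule out adjustment. This stands; the gap is that the analysis plan says nothing about CGM.
- The documents do not say when willingness is asked. Main-study consent is taken at screening, so a decision made only after months in a known arm is an inference. This stands, although attendance at the CGM visit is still after randomisation.
- Some features support balanced uptake: the gift card is open to both arms, return by mail and re-insertion are allowed, and controls are offered sessions partly to even out contact. These reduce the risk but do not show what uptake will be.
- The direction is not fixed. Engaged controls may also wear the sensor more often, in which case the biases cancel in part or reverse, as the table shows.
- CGM is not a listed outcome and carries no power claim. This stands and limits the importance of the point.

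**Conclusion.** The concern holds in a limited form. The CGM comparison is under-specified: one opt-in measurement, no analysis set, no covariates and no account of non-wearers, while the analysis method used for the other outcomes cannot be carried over.

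The missing CGM baseline is a loss of precision, not a source of bias. Adjustment for baseline HbA1c, baseline fasting glucose and sex would recover about 5 to 20% of the standard error, on the assumption of a joint correlation of 0.3 to 0.6. It also removes imbalance among wearers on those covariates. It does not remove selection on what happens after randomisation, such as success with the diet.

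Selection bias is possible but of unknown size and direction. With wearer-minus-non-wearer differences of up to 0.5 SD it is at most 0.05 SD at 95% uptake in both arms. It reaches 0.30 SD at 80% and 60% uptake if selection runs in opposite directions. Nothing in the documents says which case applies, so no single figure should be attached to it.

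**What to change.** In section 13.B.2, and in the outcome list in section 4.B.3:

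1. List CGM mean 24-h glucose and the other CGM measures as exploratory.
2. Analyse each by linear regression on arm, adjusted for baseline HbA1c, baseline fasting glucose and sex (the randomisation stratum). Name which baseline HbA1c is used, since screening samples go to one laboratory and randomisation samples to another.
3. Report wear rates by arm, and baseline characteristics of wearers and non-wearers by arm.
4. Show the 6-month HbA1c effect in wearers beside that in all randomised participants. A clear gap would point to selection; agreement is reassuring but not proof, particularly for variability measures.
5. Keep any weighting or imputation for non-wearers as a sensitivity analysis with few predictors. Imputation from 6-month HbA1c and fasting glucose suits mean glucose only. Section 2.I itself notes that HbA1c does not capture short-term excursions or variability, so it does not suit MAGE, SD or CV. It is also not possible for participants lost before month 6 (about 150 × 0.05 = 7.5 on the plan's follow-up assumption).

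The cost is a few sentences and modest programming. The covariates are already scheduled for all participants, and no visit, sensor or participant is added. The regression spends a few degrees of freedom. Any weighting may widen the interval, which is a reason to keep it out of the main CGM analysis.

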We propose to conduct a *randomized controlled trial* aimed at testing the effect of a behavioral intervention that promotes *reduced carbohydrate intake and increased consumption of heart-healthy unsaturated fats and protein* in patients with HbA1c 6.0–6.9% (**Figure 1**). We plan to recruit 150 individuals with elevated HbA1c and randomly assign them to a moderately intensive intervention on diet pattern,⁹⁷ using well-established methods for behavioral modification, or to usual diet. We will compare the difference between the active intervention and control groups for change in HbA1c from baseline to 6 months of follow-up (primary outcome). We will assess four major secondary outcomes: fasting plasma glucose, systolic BP, total-to-HDL cholesterol ratio, and body weight. In addition, we will look at several other exploratory outcomes: insulin and HOMA-IR, diastolic BP, waist circumference, and estimated CVD risk, as estimated by the 2013 ACC/AHA risk equation. The main trial components are summarized in **Table 1**.

Figure 1. Study Design

[figure not shown]

Table 1. Study Overview

Study Design	Randomized controlled trial
Study Participants	150 participants with elevated HbA1c (6.0–6.9%)
Intervention Group (n=75)	Behavioral modification to reduce carbohydrate consumption and promote consumption of foods such as non-starchy vegetables, plant-based unsaturated oils, nuts and seeds, avocados, eggs, seafood, poultry, lean meat and tofu. We will recommend moderate consumption of cheese, unsweetened Greek yogurt, and low-carb milk. If consuming higher-carbohydrate items, recommend legumes, fruits, (limited) whole grains. Target <40 g net carbohydrates per day for first 3 months and will have a goal of <40 net g carbohydrates per day; <60 g net carbohydrates per day for months 4 onwards.
Usual Diet Group (n=75)	No dietary intervention. To encourage continued participation in the trial, we will offer optional monthly educational sessions on unrelated topics, such as retirement planning or health insurance
Outcome Measures	Primary: HbA1c; Secondary: fasting plasma glucose, systolic BP, total-to-HDL-cholesterol ratio, and body weight

4.B. Study outcomes

4.B.1. Primary outcome: The primary outcome will be the difference between the intervention group and the usual diet group for change in HbA1c from baseline to 6 months. Changes in HbA1c will be calculated from blood samples taken at baseline and 6 months.

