10.B.3. Assessment and management of adverse effects: At RZ, 3-month visit, and 6-month TV, we will administer *symptom questionnaires*, which will consist of a checklist to identify participant complaints. Prior studies of low-carbohydrate dietary interventions suggest that participants may experience a range of adverse effects, including constipation, halitosis, fatigue, headache, thirst, polyuria, and nausea. Severe adverse events will be promptly reported to the DSMB. Management of adverse effects will be based on the protection and safety of the participant. If severe adverse effects are reported by a participant, carbohydrate intake will be examined and altered in order to mitigate the adverse effect. In any extreme cases, participants will be instructed to stop the intervention. As this is a behavioral intervention, adverse effects should be rare.

10.B.4. BP and anthropometric measures: BP will be measured 3 times at the screening visit and at each follow-up visit. To minimize random error, averages of the measurements at the screening and randomization visits will be taken. BP will be measured by a standard automated blood pressure measurement device (OMRON HEM-907 XL Professional Digital Blood Pressure Monitor) and performed by experienced staff, trained and certified in BP measurement. Prior to BP measurements, participants will be asked to rest quietly in a seated position with their feet supported for at least 5 minutes; staff members will use an appropriate cuff size over a bare arm. Trained and certified staff will measure weight using a calibrated balance beam scale at the screening visits, and follow-up visits. Weight and height will be measured at the RZ, and weight will also be measured at the subsequent visits.

10.B.5. Blood samples: For SV, participants will not need to fast. For RZ, 3-month visit, and 6-month TV, participants will be instructed to fast for 12 hours prior to blood sample collection. At SV, blood samples will be collected to measure HbA1c, hemoglobin, and serum creatinine. At RZ, fasting blood samples will be collected and stored as serum/plasma, whole blood aliquots and buffy coats at -80°C for future analyses, including measurement of glucose, insulin and lipids, and potential future metabolomics or genetic analyses. At 3-month visit and 6-month TV,

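### The hemoglobin exclusion is printed in mg/dL in all three places, which contradicts its own anemia label and, read literally, excludes nobody

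*Combined protocol and SAP*

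**What the plan says.** The hemoglobin exclusion appears three times in the combined protocol and SAP, each time with the same number and unit.

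- Section 6.A (Eligibility criteria), under "Factors that may affect HbA1c": "Hemoglobin <11 mg/dL (cutpoint for moderate-to-severe anemia, which could lead to falsely elevated or lowered HbA1c".
- Section 10.A.1 (Screening/baseline visits), which says how the screening results are used: "These blood samples will be used for excluding individuals with HbA1c <6.0 or >6.9". The sentence goes on to eGFR and ends "or hemoglobin <11 mg/dL".
- Section 16.A.1 (Risks to the subjects), which repeats the section 6.A list with the same hemoglobin entry, "Hemoglobin <11 mg/dL (cutpoint for moderate-to-severe anemia", and the same anemia description.

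Section 10.B.5 places the measurement at the screening visit: "At SV, blood samples will be collected to measure HbA1c, hemoglobin, and serum creatinine". Section 10.A.1 also allows a hemoglobin value from medical records of the past 3 months to be used instead. Section 4.B.1 defines the endpoint that the criterion is meant to protect: "The primary outcome will be the difference between the intervention group and the usual diet group for change in HbA1c from baseline to 6 months".

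**The concern.** The criterion describes one quantity in two ways that cannot both be right. In words it is a cutpoint for moderate-to-severe anemia. In figures it is a concentration far below anything a participant could have. No other section gives the cutoff in another unit, so a reader cannot settle the conflict by cross-reference.

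This is an operative threshold rather than background text, because section 10.A.1 is the rule that staff apply to the screening blood result. It is also the only stated screen for anemia. The other HbA1c-related exclusions rest on self-report (blood donation or transfusion, and HIV), and the reflex assay in section 10.B.5 deals with hemoglobin variants. HbA1c is both the entry criterion (6.0–6.9%) and the primary outcome. A criterion intended to keep HbA1c interpretable should be enforceable as printed.

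**Working it through.** **Inputs.** The cutoff is 11 mg/dL (sections 6.A, 10.A.1 and 16.A.1). The conversion is 1 g = 1,000 mg. The documents give no range of hemoglobin values, so 3 to 17 g/dL is used here as a deliberately wide assumption.

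**Step 1: convert the printed cutoff.** 11 mg/dL ÷ 1,000 = 0.011 g/dL.

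**Step 2: apply the printed rule (exclude if below 11 mg/dL) to assumed values, and compare it with the same number read in g/dL.**

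| Assumed hemoglobin, g/dL | In mg/dL (× 1,000) | Ratio to 11 mg/dL | Excluded as printed? | Excluded if 11 is read in g/dL? |
|---|---|---|---|---|
| 3 | 3,000 | 272.7 | No | Yes |
| 5 | 5,000 | 454.5 | No | Yes |
| 7 | 7,000 | 636.4 | No | Yes |
| 8 | 8,000 | 727.3 | No | Yes |
| 10 | 10,000 | 909.1 | No | Yes |
| 11 | 11,000 | 1,000.0 | No | No |
| 12 | 12,000 | 1,090.9 | No | No |
| 17 | 17,000 | 1,545.5 | No | No |

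As printed, the rule excludes no value in the range. With the same number in g/dL, the cutoff would be 11,000 mg/dL, exactly 1,000 times the printed one, and the rule would separate low values from higher ones, as the anemia label implies.

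**Step 3: look for a correction elsewhere.** Table 4 schedules hemoglobin at the screening visit only and gives no unit. Section 10.B.5 gives no cutoff. No section states the threshold differently.

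**Step 4: check for knock-on effects.** The sample size in section 12 rests on the SD of change in HbA1c (0.35%), the detectable difference (0.17%), 80% power and 95% follow-up; the text on Table 5 adds a two-sided alpha of 0.05. Hemoglobin enters none of these, so sample size and power do not change.

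**The case against.** The strongest reply is that nobody would be misled. The number and the purpose are both clear, and only the unit prefix is wrong. Staff who compare 11 with a laboratory report in its usual unit would probably screen as intended, and in doing so they would follow the criterion's own words and contradict only its unit. The section 16.A.1 list repeats the section 6.A list almost word for word, and section 10.A.1 restates the same cutoffs, so this is most plausibly one slip carried forward and not three separate errors. Section 7.B also has the coordinator resolve outliers before enrollment.

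Most of this stands, and it limits the consequence. It does not remove the contradiction: the unit is wrong against the label in every place, including the rule applied at screening.

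A reader might go further and infer that anemic participants enter the trial and leave the primary outcome unprotected. The documents do not support that. They do not describe a database eligibility field, its unit or an automated check, and they do not show how the rule was applied. A check that compares the reported number with 11 would work as intended if results are entered in g/dL. Even if some anemic participants were enrolled, the endpoint is a randomized comparison of change scores. A stable distortion of HbA1c would partly cancel between baseline and 6 months, and randomization would be expected to spread the remainder across both arms, mainly as noise.

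**Conclusion.** The point holds as a unit error in an operative eligibility threshold. The printed cutoff is 1,000 times lower than the same number in g/dL. Read literally, it excludes nobody and contradicts the protocol's own description of the figure.

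The correction is minor but real. The conclusion that the rule excludes nobody rests on the unit conversion and on the assumption that every screened person has a hemoglobin of at least 3 g/dL. That the slip lies in the unit is an inference from the anemia label, because no section gives the cutoff in g/dL.

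No number of affected participants can be given. The documents report neither the frequency of anemia in the screened population nor how the rule was applied. An actual effect on the primary outcome is therefore not established.

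**What to change.** Reconcile the unit with the stated anemia label in sections 6.A, 10.A.1 and 16.A.1 so that all three agree. The label points to g/dL, and the sponsor should confirm this against the source of the cutpoint.

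Then confirm that the screening form, the manual of procedures and any database eligibility check use the unit the laboratory reports. This should cover hemoglobin values taken from medical records. If participants have already been enrolled, a single check of their recorded screening hemoglobin values would show whether the slip had any effect.

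The text change is one unit in three places and could be made by administrative amendment. It needs no change to the design, the sample size or the analysis.
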